13.3 Patient Informed Consent

All information about the clinical study, including the patient information and the ICF, is prepared and used for the protection of the human rights of the patient according to ICH GCP guidelines and the Declaration of Helsinki.

It is the responsibility of the investigator to obtain signed ICFs from each patient participating in this study after adequate explanation of the aims, methods, objectives, and potential hazards of the study and prior to undertaking any study-related procedures.

The ICF, prepared by the investigator with the assistance of the sponsor, must be approved along with the study protocol by the IEC/IRB and be acceptable to the sponsor.

The patient must be provided with the patient information and ICF consistent with the study protocol version used and approved by the relevant IEC/IRB. The ICF must be in a language fully comprehensible to the prospective patient. Patients (and/or relatives, guardians, or legal representatives, if necessary) must be given sufficient time and opportunity to inquire about the details of the study and to discuss and decide on their participation in the study with the investigator concerned. The patient and the person explaining about the study and with whom they discuss the informed consent will sign and date the ICF. A copy of the signed ICF will be retained by the patient and the original will be filed in the investigator file unless otherwise agreed.

13.4 Study Monitoring

A monitor will contact and visit the investigator at the study center prior to the entry of the first patient and as necessary during the study until after the last patient has completed. A monitor will also perform a study closure visit.

In accordance with ICH GCP guidelines, the investigator must ensure provision of sufficient time, reasonable space, and adequate qualified personnel for the monitoring visits. The visits are for the purpose of verifying adherence to the study protocol and the completeness, consistency, and accuracy of data entered on the eCRF and other documents.

The investigator will make all source data (i.e., the various study records, the eCRFs, laboratory test reports, other patient records, drug accountability forms, and other pertinent data) available for the monitor and allow access to them throughout the entire study period. Monitoring is done by comparing the relevant site records of the patients with the entries on the eCRF (i.e., source data verification). It is the monitor's responsibility to verify the adherence to the study protocol and the completeness, consistency, and accuracy of the data recorded on the eCRFs.

By agreeing to participate in the study, the investigator agrees to cooperate with the monitor to ensure that any problems detected in the course of the monitoring visits are resolved. Contact information for the study monitor is located in the investigator file. Representatives from Clovis may also contact and visit the investigators and monitor data during the study.

13.5 Case Report Form

The data will be collected using an electronic data capture (EDC) system by remote data entry on eCRFs. Sites will receive training on the EDC system. All users will be supplied with unique login credentials.

Prior to study start, the investigator will prepare a list showing the signature and handwritten initials of all individuals authorized to make or change entries on eCRFs. This "study center personnel and delegation list" must be kept current throughout the study.

For each patient enrolled, an eCRF must be completed and reviewed by the principal investigator or co-investigator within a reasonable time period (< 2 weeks) after data collection. This also applies to records for those patients who fail to complete the study. If a patient withdraws from the study, the reason must be noted on the eCRF. If a patient is withdrawn from the study because of a treatment-limiting AE, thorough efforts should be made to clearly document the outcome.

All laboratory data and investigator observations on the results and any other clinically significant test results must be documented on eCRFs.

Full information regarding EDC and completing eCRFs is included in the investigator files. All questions or comments related to electronic capture should be directed to the assigned monitor.

13.6 Study Termination and Site Closure

Both the sponsor and the investigator reserve the right to terminate the study at any time. Should this be necessary, both parties will arrange discontinuation procedures. In terminating the study, Clovis and the investigator will assure that adequate consideration is given to the protection of the patients' interests.

Clovis reserves the right to discontinue the study at any time for medical or administrative reasons. When feasible, a 30-day written notification will be given.

The entire study will be stopped if:

- The protocol-specified treatment is considered too toxic to continue the study
- Evidence has emerged that, in the opinion of the sponsor or the investigator(s), makes the continuation of the study unnecessary or unethical
- The stated objectives of the study are achieved
- The sponsor discontinues the development of PO CO-1686

Regardless of the reason for termination, all data available for the patient at the time of discontinuation of follow-up must be recorded on the eCRF. All reasons for discontinuation of treatment must be documented. In terminating the study, the investigator will ensure that adequate consideration is given to the protection of the patients' interests.

13.7 Modification of the Study Protocol

Protocol amendments, except when necessary to eliminate an immediate hazard to patients, must be made only with the prior approval of Clovis. Agreement from the investigator must be obtained for all protocol amendments and amendments to the informed consent document. The IEC/IRB must be informed of all amendments and give approval prior to their implementation. The sponsor will submit any study protocol amendments to the concerned regulatory authorities for approval and keep the investigator(s) updated as detailed in the ICH GCP guidelines.

13.8 Retention of Study Documents

The study site will maintain a study file, which should contain, at minimum, the Investigator's Brochure, the protocol and any amendments, drug accountability records, correspondence with the IEC/IRB and Clovis, and other study-related documents.

The investigator agrees to keep records and those documents that include (but are not limited to) the identification of all participating patients, medical records, study-specific source documents, source worksheets, all original signed and dated ICFs, copies of all eCRFs, query responses, and detailed records of drug disposition to enable evaluations or audits from regulatory authorities and Clovis or its designees.

The investigator shall retain records required to be maintained for a period of 5 years following the date a marketing application in an ICH region is approved for the drug for the indication for

which it is being investigated or, if no application is to be filed or if the application is not approved for such indication, until at least 5 years after the investigation is discontinued. However, these documents should be retained for a longer period if required by the applicable regulatory requirement(s) or if needed by Clovis. In addition, the investigator must make provision for the patients' medical records to be kept for the same period of time.

No data should be destroyed without the agreement of Clovis. Should the investigator wish to assign the study records to another party or move them to another location, Clovis must be notified in writing of the new responsible person and/or the new location. Clovis will inform the investigator, in writing, when the trial-related records are no longer needed.

Patients' medical records and other original data will be archived in accordance with the archiving regulations or facilities of the investigational site.

13.9 Clinical Study Report

A clinical study report will be prepared under the responsibility and supervision of Clovis and signed by the sponsor's chief medical officer, thereby indicating their agreement with the analyses, results, and conclusions of the clinical study report.

13.10 Study Publication

All data generated from this study are the property of Clovis and shall be held in strict confidence along with all information furnished by Clovis. Independent analysis and/or publication of these data by the investigator(s) or any member of their staff are not permitted without the prior written consent of Clovis. Written permission to the investigator will be contingent on the review by Clovis of the statistical analysis and manuscript, and will provide for nondisclosure of Clovis confidential or proprietary information. In all cases, the parties agree to submit all manuscripts or abstracts to all other parties 30 days prior to submission. This will enable all parties to protect proprietary information and to provide comments based on information that may not yet be available to other parties.

13.11 Quality Assurance Audits

An audit visit to clinical centers may be conducted by a quality control auditor appointed by Clovis. The purpose of an audit, which is independent of and separate from routine monitoring or quality control functions, is to evaluate trial conduct and compliance with the protocol, SOPs, ICH GCPs, and the applicable regulatory requirements. The investigator and the sponsor may also be subject to an inspection by FDA, European Regulatory authorities, or other applicable regulatory authorities at any time.

The auditor and regulatory authorities will require authority from the investigator to have direct access to the patients' medical records. It is important that the investigator(s) and their staff cooperate with the auditor or regulatory authorities during this audit or inspection.

15 APPENDICES

Appendix A. Response Evaluation Criteria in Solid Tumors Criteria

Appendix B. Eastern Cooperative Oncology Group Performance Status Scale

Appendix C. Study CO-1686-019 Extension Phase

Appendix A

Response Evaluation Criteria in Solid Tumors Criteria

The RECIST guidelines (Version 1.1) are described in Eisenhauer (2009)¹¹ and at <http://www.eortc.be/Recist/Default.htm>. A short summary is given below.

Measurable Disease:

Tumor lesions: measurable lesions are defined as those that can be accurately measured in at least one dimension (longest diameter to be recorded) with the following:

1. A minimum size of 10 mm by CT scan (CT scan thickness no greater than 5 mm).
2. A minimum size of 10 mm caliper measurement by clinical exam (lesions that cannot be accurately measured with calipers should be recorded as nonmeasurable).
3. A minimum size of 20 mm by chest X-ray.

All tumor measurements must be recorded in millimeters (or decimal fractions of centimeters).

Malignant lymph nodes: to be considered pathologically enlarged and measurable, a lymph node must be ≥ 15 mm in short axis when assessed by CT scan (CT scan slice thickness recommended to be not greater than 5 mm). At baseline and in follow-up, only the short axis will be measured and followed.

Nonmeasurable Disease:

All other lesions (or sites of disease), including small lesions (longest diameter < 10 mm or pathological lymph nodes with ≥ 10 to < 15 mm short axis), as well as truly nonmeasurable lesions, are considered nonmeasurable disease. Lesions considered truly nonmeasurable include leptomeningeal disease, ascites, pleural/pericardial effusions, inflammatory breast disease, lymphangitic involvement of skin and lung, and abdominal masses/abdominal organomegaly identified by physical exam that is not measurable by reproducible imaging techniques.

Bone Lesions

Bone lesions, cystic lesion, and lesions previously treated with local therapy require particular comment. Bone scan, PET scan, or plain films are not considered adequate imaging techniques to measure bone lesions. However, these techniques can be used to confirm the presence or disappearance of bone lesions.

Lytic bone lesions or mixed lytic–blastic lesions with identifiable soft tissue components that can be evaluated by cross-sectional imaging techniques such as CT or MRI can be considered as measurable lesions if the soft tissue component meets the definition of measurability described above.

Blastic bone lesions are nonmeasurable.

Cystic Lesions

Lesions that meet the criteria for radiographically defined simple cysts should not be considered as malignant lesions (neither measurable nor nonmeasurable) because they are, by definition, simple cysts.

Cystic lesions thought to represent cystic metastases can be considered as measurable lesions if they meet the definition of measurability described above. However, if noncystic lesions are present in the same patient, these are preferred as target lesions.

Lesions with Prior Local Treatment

Tumor lesions situated in a previous irradiated area or in an area subjected to other locoregional therapy are usually not considered measurable unless there has been demonstrated progression in the lesion.

Target Lesions

All measurable lesions up to a maximum of two lesions per organ and five lesions in total, representative of all involved organs, should be identified as target lesions and recorded and measured at baseline. Target lesions should be selected on the basis of their size (lesions with the longest diameter) and their suitability for accurate repeated measurements (either by imaging techniques or clinically). A sum of the longest diameter (LD) for all target lesions will be calculated and reported as the baseline sum LD. The baseline sum LD will be used as reference by which to characterize the objective tumor response.

Nontarget Lesions

RECIST criteria require unequivocal quantification of the changes in tumor size for adequate interpretation of the sum of target lesions. Consequently, when the boundaries of the primary are difficult to delineate, this tumor should not be considered a target lesion.

Guidelines for Evaluation of Measurable Disease

The same method of assessment and the same technique should be used to characterize each identified and reported lesion at baseline and during follow-up. Imaging-based evaluation is preferred to evaluation by clinical examination when both methods have been used to assess the antitumor effect of a treatment.

Evaluation of Target Lesions

Complete Response	Disappearance of all target lesions. Any pathological lymph nodes (whether target or nontarget) must have reduction in short axis to < 10 mm.
Partial Response	At least a 30% decrease in the sum of the LD of target lesions, taking as reference the baseline sum LD.
Stable Disease	Neither sufficient shrinkage to qualify for partial response nor sufficient increase to qualify for PD, taking as reference the smallest sum LD since the treatment started.
Progressive Disease	At least a 20% increase in the sum of the LD of target lesions, taking as reference the smallest sum on study (this includes the baseline sum if that is the smallest on study). In addition to the relative increase of 20%, the sum must also demonstrate an absolute increase of at least 5 mm. The appearance of one or more new lesions is also considered progression.

Evaluation of Non-target Lesions

Complete Response	Disappearance of all nontarget lesions and normalization of tumor marker level.
Stable Disease/Incomplete Response	Persistence of one or more nontarget lesion(s) or/and maintenance of tumor marker level above the normal limits.
Progressive Disease	Appearance of one or more new lesions and/or unequivocal progression of existing nontarget lesions.

If tumor markers are initially above the institutional ULN, they must normalize for a patient to be considered a complete *responder*.

Evaluation of Best Overall Response

The best overall response is the best response recorded from the start of the treatment until disease progression/recurrence (taking as reference for PD the smallest measurements recorded since the treatment started). The patient's best response assignment will depend on the achievement of both measurement and confirmation criteria.

Time Point Response

A response assessment will occur at the protocol-specified time points. The tables below provide a summary of the overall response status calculation at each time point for patients who have measureable and non-measureable disease (non-target disease only).

Time Point Response: Patients with Target (+/- Non-target) Disease			
Target Lesions	Nontarget Lesions	New Lesions	Overall Response
CR	CR	No	CR
CR	Non-CR/non-PD	No	PR
CR	Not evaluated	No	PR
PR	Non-PD or not evaluated	No	PR
SD	Non-PD or not evaluated	No	SD
Not Evaluated	Non-PD	No	NE
PD	Any	Yes or No	PD
Any	PD	Yes or No	PD
Any	Any	Yes	PD

NE = Not evaluable.

Evaluation of Best Overall Response When Confirmation of CR and PR Required		
Overall Response First Time Point	Overall Response Subsequent Time Point	Best Overall Response
CR	CR	CR
CR	PR	SD, PD or PR ^a
CR	SD	SD provided minimum criteria for SD duration met, otherwise, PD
CR	PD	SD provided minimum criteria for SD duration met, otherwise, PD
CR	NE	SD provided minimum criteria for SD duration met, otherwise, NE
PR	CR	PR
PR	PR	PR
PR	SD	SD
PR	PD	SD provided minimum criteria for SD duration met, otherwise, PD
PR	NE	SD provided minimum criteria for SD duration met, otherwise, NE
NE	NE	NE

^a If a CR is truly met at first time point, then any disease seen at a subsequent time point, even disease meeting PR criteria relative to baseline, makes this disease PD at that point (since disease must have reappeared after CR). Best response would depend on whether minimum duration for SD was met. However sometimes 'CR' may be claimed when subsequent scans suggest small lesions were likely still present and in fact the patient had PR, not CR at the first time point. Under these circumstances, the original CR should be changed to PR and the best response is PR.

Missing Assessments and Not Evaluable Designation

When no imaging/measurement is done at all at a particular time point, the patient is not evaluable (NE) at that time point. If only a subset of lesion measurements are made at an assessment, usually the case is also considered NE at that time point, unless a convincing argument can be made that the contribution of the individual missing lesion(s) would not change the assigned time point response, which is most likely to occur in the case of PD; eg, if only 2 of 3 baseline target lesions are assessed and result in a > 20% increase in the sum, then the patient would be assessed as a PD regardless of the missing lesion.

Patients with a global deterioration of health status requiring discontinuation of treatment without objective evidence of disease progression at that time should be classified as having symptomatic deterioration. Every effort should be made to document the objective progression, even after discontinuation of treatment.

In some circumstances, it may be difficult to distinguish residual disease from normal tissue. When the evaluation of CR depends on this determination, it is recommended that the residual lesion be investigated (fine needle aspiration/biopsy) prior to confirming the complete response status.

Confirmatory Measurement/Duration of Response

Confirmation

CT scans are required every 8 ± 1 weeks. If an initial CR or PR is noted, confirmatory scans must be performed 4 ± 1 week later. In the case of SD, follow-up measurements must have met the SD criteria at least once after study entry at a minimum interval of no less than 4 ± 1 weeks.

Duration of Overall Response

The duration of overall response is measured from the time measurement criteria are met for CR or PR (whichever is first recorded) until the first date that recurrent or PD is objectively documented (taking as reference for PD the smallest measurements recorded since the treatment started).

The duration of overall CR is measured from the time measurement criteria are first met for CR until the first date that recurrent disease is objectively documented.

Duration of Stable Disease

SD is measured from the start of the treatment until the criteria for progression are met, taking as reference the smallest measurements recorded since the treatment started.

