5.1.2 Treatment Period

CO-1686 will be administered to patients BID (see [Section 7.3](#)). Patients will take CO-1686 with a meal or within 30 minutes after a meal. Treatment with CO-1686 is continuous, except where delayed or reduced according to protocol-specified toxicity criteria ([Section 7.4](#)). Each 28-day period of treatment will represent 1 cycle, with dosing initiated on C1D1. No dose escalation beyond the starting dose is allowed in either cohort. The counting of all 28-day cycles should start from C1D1.

Patients will undergo serial assessments for anti-tumor efficacy, drug safety, and PRO. Sparse blood sampling for POPPK analyses will be conducted in all patients treated with CO-1686. Serial blood sampling for longitudinal quantitative assessment of ctDNA will be conducted.

Tumor scans will be acquired by the investigative site and evaluated locally for patient treatment decisions; however, copies of all tumor scans will be sent to a central radiological vendor. In Cohort A, scans will be assessed by IRR for the primary endpoint evaluation. In Cohort B, scans will be assessed by IRR if needed as a supporting analysis. Protocol-specified treatment will continue until there is RECIST version 1.1 or clinical tumor progression or unacceptable toxicity as assessed by the investigator. Following disease progression on CO-1686 and discontinuation of protocol-specified treatment, patients who provide additional consent will undergo tumor biopsy before subsequent-line therapy is initiated. After discontinuation of protocol-specified treatment, subsequent anticancer therapy will be recorded.

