9.2 Treatment Period

Before enrolling a patient, all eligibility criteria must be satisfied.

Patients will take CO-1686 625 mg BID (Cohort A) or 500 mg BID (Cohort B), as directed. PO CO-1686 should be taken with 8 oz (240 mL) of water and with a meal or within 30 minutes after a meal. Patients will record the dose and timing of administration of PO CO-1686 in their daily dosing patient diary.

Unless otherwise specified, all patients in Cohorts A and B will undergo the following procedures and assessments. All procedures and assessments are to be completed at the

scheduled time point and the timing of all scans should be determined based on the date of C1D1 of PO CO-1686 treatment.

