9.2.5 Cycle 2 Day 15 (± 1 Day)

- Fasting glucose (local laboratory)

9.2.6 Cycle 2 (Day 1, Occurring 28 ± 3 Days After C1D1) and Cycle 3+ (Day 1, Every 28 ± 3 Days Thereafter, Counting from C1D1)

The following procedures will be performed at 28 ± 3 day intervals:

- Physical examination
- Weight
- ECOG performance status
- Vital signs (blood pressure, pulse, and temperature)
- 12-lead ECG (in triplicate, 10-sec tracings > 2 min apart)
- Fasting serum chemistry (including fasting glucose). HbA1c will be measured every other cycle (Day 1 of Cycle 3, 5, 7 etc).
- Hematology (including reticulocyte count).
- Blood sampling for biomarker/EGFR mutational testing and exploratory research
- Serum alpha-1 acid glycoprotein (AAG) samples and PK blood sample (Cycle 2 – 7 only; [Section 9.5.3](#))
- Concomitant medication and procedures since last visit
- AE monitoring
- Collection and review of patient diary and CO-1686 drug return
- QoL questionnaires (EORTC QLQ-C30, EORTC QLQ-L13, and the DLQI) – at 8 ± 1 weeks for 6 months (Day 1 of Cycle 3, 5, 7, ± 1 weeks inclusive). After Cycle 7, questionnaires will be collected every 12 ± 1 weeks (Day 1 of Cycle 10, 13, 16 etc ± 1 weeks) and at end-of-treatment
- CO-1686 tablets will be dispensed to the patient; patient diary will be provided to the patient
- Tumor assessments will be performed every 8 ± 1 weeks (Day 1 of Cycle 3, 5, 7 etc ± 1 week) after dosing until tumor progression (see [Section 9.5.2.1](#)).

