9.5.2 Efficacy Evaluations

9.5.2.1 Tumor Assessments

Tumor assessments will be performed at Screening, and every 8 ± 1 weeks thereafter (Day 1 of Cycle 3, 5, 7 etc ± 1 week) until tumor progression, including at the End-of-Treatment Visit, if disease progression has not been documented previously. For patients with clinical progression, radiographic assessment should be performed to document evidence of radiographic progression. For a patient who discontinues treatment before progression, scans should continue until progression according to the protocol schedule. Exceptions to this requirement may be acceptable based on local institutional or regulatory requests and must be approved in advance by the sponsor. Scans will be evaluated locally for patient treatment decisions. Scans will be sent to a central radiological laboratory for independent response evaluation. In Cohort B, scans will be held at the central radiological vendor for later evaluation, assessed by IRR, if needed as a supporting analysis. Tumor response will be interpreted using RECIST Version 1.1 ([Appendix A](#)).¹¹

Patients who continue treatment with CO-1686 post-progression should continue to be scanned according to the protocol until they discontinue from the study.

Patients are required to have an end-of-treatment tumor scan using the same methodology used at Screening, **unless:**

- a) **Patient has radiographic evidence of disease progression while on study**
- or**
- b) **It has been < 2 weeks since last on-study scan**

In addition, an MRI may be used in place of CT at the end-of-treatment scan if required per local authorities.

Tumor assessments should consist of clinical examination and appropriate imaging techniques (preferably CT scans of the chest and abdomen, with appropriate slice thickness per RECIST Version 1.1); other studies (MRI and X-ray) may be performed if required. Imaging of the pelvis is required if clinically indicated eg, prior site of metastasis or symptomatic. The same methods used to detect lesions at baseline are to be used to follow the same lesions throughout the clinical study.

Brain imaging is required at baseline. In Cohort A, patients with brain lesions at baseline will require repeat brain imaging as part of the follow-up tumor assessments. In Cohort B, patients with brain lesions at Screening are not eligible for the study. Patients without baseline brain lesions do not require brain imaging on study unless clinically indicated.

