#### 9.1 Primary Efficacy Analysis

The primary efficacy endpoint of ORR is defined as a best response of CR or PR as determined by the independent radiological review. Response and/or progression are evaluated using the RECIST 1.1 criteria. The ORR will be summarized with frequencies and percentages. The ORR is the best overall response recorded from the start of the treatment until disease progression or the time of the data cutoff. The frequency and percentages of patients with a best overall response of complete response (CR), partial response (PR), stable disease (SD), or progressive disease (PD) will be summarized.

The confirmed response rate will be calculated for patients with sufficient data to determine if the patient has a confirmed response or has progressive disease, otherwise patients will be classified as inevaluable for confirmed response at the time of analysis.

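### Appendix A calls for a confirming scan 3 to 5 weeks after a first CR or PR, but Section 9 schedules none and the SAP gives no interval, so it is open which responses are confirmed and whether the primary ORR is a confirmed rate

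*Protocol*

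**What the plan says.** **Protocol Appendix A** gives confirmation a deciding role: "The patient's best response assignment will depend on the achievement of both measurement and confirmation criteria". Under its confirmation heading it sets the routine interval, "CT scans are required every 8 ± 1 weeks", and then adds: "If an initial CR or PR is noted, confirmatory scans must be performed 4 ± 1 week later". Its table for best response with confirmation required works differently. It pairs the response at a first time point with the response at a subsequent one and gives no interval. PR followed by PR is PR; PR followed by SD is SD. The stable disease rule in the same appendix is written as a minimum interval of 4 ± 1 weeks.

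**Protocol schedule.** Section 9.5.2.1 places scans at Screening and "every 8 ± 1 weeks thereafter (Day 1 of Cycle 3, 5, 7 etc ± 1 week) until tumor progression", with an end-of-treatment scan unless there was radiographic progression on study or the last scan was under 2 weeks before. The synopsis, Table 9-1 with its scan footnote, and Section 9.2.6 agree. They also cover scans for clinical progression and for patients who stop before progression. None lists a confirmatory scan.

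**Protocol 11.2.4.1** describes ORR through the best overall response recorded up to progression or recurrence and does not mention confirmation.

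**SAP 9.1** counts a patient in the primary ORR when the best response by independent review is CR or PR. It then adds a further quantity: "The confirmed response rate will be calculated for patients with sufficient data to determine if the patient has a confirmed response or has progressive disease". The remaining patients are labelled inevaluable for confirmed response. No interval is given. SAP 9.2.1 repeats this for the investigator assessment.

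**The concern.** A site that works from Table 9-1 will not obtain the scan that Appendix A says must be done. A site that also reads Appendix A will. Confirmation would then be ascertained differently across sites in an open-label, single-arm trial whose primary endpoint is response.

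The analysis text does not settle the matter. It leaves two questions open:

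- Does a response seen again at the next routine scan count as confirmed?
- Is the primary ORR a confirmed rate, as Appendix A implies, or an unconfirmed one, as SAP 9.1 suggests by reporting the confirmed rate separately?

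Different answers can give different primary results from the same scans.

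**Working it through.** **1. Inputs**

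- Cycle length 28 days (Protocol 5.1.2): "Each 28-day period of treatment will represent 1 cycle, with dosing initiated on C1D1".
- Scans on Day 1 of Cycles 3, 5, 7 and so on, ± 7 days (Protocol 9.5.2.1).
- Scan anchor (Protocol 9.2): "the timing of all scans should be determined based on the date of C1D1".
- Visit window ± 3 days (Protocol 9.2.6): "The following procedures will be performed at 28 ± 3 day intervals". It is used only for the most permissive reading below.
- Confirmation window 4 ± 1 weeks (Appendix A).
- End-of-treatment visit 28 ± 7 days after last dose (Table 9-1).

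**2. The plan's own interval.** Two cycles are 2 × 28 = 56 days = 8.0 weeks, which reproduces the stated 8-week spacing.

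**3. Confirmation window.** 28 ± 7 = 21 to 35 days after the first CR or PR.

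**4. Gap between consecutive routine scans**

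| Reading | Formula (days) | Gap (days) | Shortest gap minus 35 |
|---|---|---|---|
| Each scan timed from C1D1, ± 7 | 56 ± 2 × 7 | 42 to 70 | 7 days |
| Each scan timed from the previous one, ± 7 | 56 ± 7 | 49 to 63 | 14 days |
| Visit and scan windows stacked, ± (3 + 7) | 56 ± 2 × 10 | 36 to 76 | 1 day |

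No reading overlaps 21 to 35 days. The first row follows Section 9.2.

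**5. End-of-treatment scan.** Let the last dose fall d days after the responding scan. The visit then falls at d + 28 ± 7 days.

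- At the nominal 28 days, 21 ≤ d + 28 ≤ 35 gives −7 ≤ d ≤ 7.
- Using the full ± 7 days, −14 ≤ d ≤ 14.

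A gap of 21 to 35 days exceeds the 2-week exemption. The scan is therefore due if there was no radiographic progression, and it can confirm. This applies only to responders who stop close to the responding scan.

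**6. Two patients under each passage**

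| Passage | PR at week 8, PR at week 16 | PR at week 8, SD at week 16 |
|---|---|---|
| Appendix A sentence, if it limits which scans count | Not confirmed (56 days > 35) | Not confirmed |
| Appendix A table | PR | SD |
| Protocol 11.2.4.1, on its own words | Responder | Responder |
| SAP 9.1, ORR | Responder | Responder, unless Appendix A is read in |
| SAP 9.1, confirmed rate | Not settled: no interval | Not confirmed, or inevaluable |

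**7. Possible size.** The 40% row of Table 11-1 corresponds to 50 of 125 patients, with a stated CI of 31 to 49. Let k be the number of the 50 whose response is repeated only at the next routine scan. The documents give no value, so k is an assumption.

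- Counted as not confirmed: (50 − k)/125.
- Dropped as inevaluable: (50 − k)/(125 − k).

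| k | Next routine scan confirms | Not confirmed | Dropped as inevaluable |
|---|---|---|---|
| 0 | 40.0% | 40.0% | 40.0% |
| 5 | 40.0% | 45/125 = 36.0% | 45/120 = 37.5% |
| 12 | 40.0% | 38/125 = 30.4% | 38/113 = 33.6% |
| 25 | 40.0% | 25/125 = 20.0% | 25/100 = 25.0% |

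Each such patient moves the second rate by 1/125 = 0.8 percentage points. With k = 12 it falls below the stated lower limit of 31%.

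**The case against.** The strongest reply is that the two rules can coexist. Appendix A states them in adjacent sentences, and the natural reading is a routine 8-weekly scan plus an extra scan triggered by response. Section 9.5.2.1 sends the reader to Appendix A for interpreting response, so a site that follows the whole protocol can confirm responses on time. On this view the defect is a missing line in Section 9. That much stands, and it rules out calling the endpoint unworkable. It does not remove the problem: the sections a site uses for scheduling omit the scan, and the analysis text does not say what happens when it was not done.

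A reader might infer that no scheduled scan can ever confirm a response, or that the confirmed ORR would fall to near zero. The documents do not support either reading. The end-of-treatment scan is scheduled and can fall in the window. The Appendix A sentence says when a scan is to be done; it does not say that a later repeat response fails to confirm. The Appendix A table accepts PR followed by PR with no upper limit.

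A reader might also infer that a patient with two consecutive PRs is inevaluable under the SAP. SAP 9.1 keeps that label for patients without sufficient data at the time of analysis, in a plan written around a data cutoff. The weakness is that sufficient data is not defined, so such a patient is neither clearly included nor clearly excluded.

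Amendment 5 replaces the Section 9 schedules for ongoing patients and ends the required central submission of scans. What remains at issue is mainly how data already collected are classified.

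**Conclusion.** The concern holds as an inconsistency between Appendix A, Section 9 and the two analysis sections. Routine scans are 6 to 10 weeks apart when timed from C1D1 and cannot meet a 3-to-5-week window; the margin is 7 days on that reading and 1 day on the most permissive one. Confirmation inside the window needs an unscheduled response-triggered scan or, narrowly, an end-of-treatment scan.

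Whether a response is confirmed, and whether the primary ORR is a confirmed rate, depends on which passage is followed. The numerical effect cannot be fixed from the documents. It is 0.8 percentage points per affected responder at n = 125, and the table in the working shows a range under assumed counts. Those counts are illustrations, not forecasts. No stated sample size, confidence interval or power figure depends on the confirmation window. The point deserves correction before the response data are analysed, and the correction is cheap.

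**What to change.** 1. **Reconcile Appendix A with Section 9.** The sponsor should decide whether the response-triggered scan is required and make the synopsis, Table 9-1, Sections 9.2.6 and 9.5.2.1 and Appendix A agree. This review does not say which rule is right.
2. **Define confirmation in Protocol 11.2.4.1 and SAP 9.1** (and 9.2.1) by a minimum interval with no upper limit, in line with the Appendix A table and the form of its stable disease rule. A CR or PR repeated at the next routine scan then counts as confirmed and is not classed as inevaluable. A minimum of 21 or 28 days is met by every next routine scan, since the shortest gap is 36 days on any reading. With 28 days, a triggered scan on days 21 to 27 would not confirm, so the text should give the figure in days.
3. **State whether the primary ORR is confirmed**, as Appendix A implies, and report the unconfirmed rate beside it.
4. **Say what counts as sufficient data** for the confirmed rate.

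The analysis changes in items 2 to 4 cost wording and one extra tabulation, and they require no additional scan. The downside is that a confirmed primary ORR may be somewhat lower than the unconfirmed rate.
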